9.1.2.5. Spondyloarthritis Research Consortium of Canada Enthesitis Index

The SPARCC enthesitis index is used to measure the severity of enthesitis, which assesses 16 sites for enthesitis using a score of “0” for no activity or “1” for activity (Maksymowych et al. 2009). The SPARCC enthesitis index is the sum of all site scores (range 0 to 16), with higher scores indicating more severe enthesitis. The sites assessed include medial epicondyle (left/right [L/R]), lateral epicondyle (L/R), supraspinatus insertion into greater tuberosity of humerus (L/R), greater trochanter (L/R), quadriceps insertion into superior border of patella (L/R), patellar ligament insertion into inferior pole of patella or tibial tubercle (L/R), Achilles tendon insertion into calcaneum (L/R), and plantar fascia insertion into calcaneum (L/R).

9.1.2.6. Juvenile Spondyloarthritis Disease Activity Index

The JSpADA is used to evaluate the disease activity of juvenile spondyloarthritis (Weiss et al. 2014). The range of possible scores is 0 to 8, where higher scores indicate more disease activity.

The Juvenile Spondyloarthritis Disease Activity Index scores will be determined by 8 components:

- Active joint count: 0 joints = 0, 1 to 2 joints = 0.5, >2 joints = 1
- Active enthesitis count: 0 entheses = 0, 1 to 2 entheses = 0.5, >2 entheses = 1
- Pain over the past week as assessed using a 0-10 NRS (0 = no pain; 10 = pain as bad as your child can imagine: 0 = 0, 1 to 4 = 0.5, 5 to 10 = 1
- CRP level related to juvenile spondyloarthritis activity: normal = 0, 1 to 2 times normal = 0.5, >2 times normal = 1
- Morning stiffness >15 minutes: Absent = 0, Present = 1
- Clinical sacroiliitis (defined as the presence of ≥ 2 of the following: tenderness on examination, positive Patrick’s test or flexion, abduction and external rotation (FABER) test, and inflammatory back pain): Absent = 0, Present = 1
- Uveitis (any uveitis including acute/symptomatic and chronic/asymptomatic disease): Absent = 0, Present = 1
- Back mobility (abnormal back mobility defined as modified Schober’s test <20 cm): Normal = 0, Abnormal = 1

9.1.2.7. Physician’s Global Assessment of Disease Activity

The Physician’s Global Assessment of Disease Activity is used to assess the patient’s current disease activity, as it relates to their signs and symptoms. The instrument uses a 21-circle VAS ranging from 0 to 10 (using 0.5 increments) where 0 = “no activity” and 10 = “maximum activity” (Filocamo et al. 2010).

9.1.3. Exploratory Efficacy Assessment

The EQ-5D-Y is a widely used, generic questionnaire that assesses health status “today” (Ravens-Sieberer et al. 2010). The first part assesses 5 dimensions (mobility, self-care, usual activities, pain/discomfort, and anxiety/depression). This part of the EQ-5D-Y can be used to

generate a health state index score, which is often used to compute a quality-adjusted life years (QALY) for utilization in health economic analyses.

9.1.4. Immunological Measurements

Potential effects of baricitinib on the cellular and humoral immune system will be evaluated through the analysis of immunoglobulin levels, immunophenotyping (including T and B cells, T-cell subsets, and natural killer cells), white blood cells (WBC), and WBC differential.

Changes from baseline in immunoglobulin levels and peripheral blood immunophenotyping (including T and B cells, T cell subsets, and NK cells) to Week 4, 12, and 44 (end of DBW period) will be assessed.

In addition, patients will be immunized with appropriate vaccinations as part of or in the course of their usual care according to the local requirement throughout the study period. When the patients become eligible for a tDaP and/or a pneumococcal conjugate vaccine during the study period, they are immunized with the vaccines and their antibody titres to the antigens will be evaluated pre-immunization and at 4 and 12 weeks post-immunization. A primary immune response will be assessed in patients who have never received tDaP or pneumococcal conjugate vaccines previously and secondary/booster responses will be assessed if the patients have previously received the vaccines.

9.1.5. Health Outcomes

Childhood Health Assessment Questionnaire

The Childhood Health Assessment Questionnaire (CHAQ) assesses health status and physical function in children with juvenile arthritis over the past week, which the parent or legal guardian completes, regardless of the age of the patient.

The CHAQ has 2 indices – the Disability Index and the Discomfort Index. The Disability Index contains 30 items grouped into the following 8 domains (not including assistive devices/aids questions): dressing and grooming, arising, eating, walking, hygiene, reach, grip, and activities. The domains are averaged to calculate the Disability Index (physical function). Each item is scored from 0 to 3 (0 = no difficulty; 1 = some difficulty; 2 = much difficulty; 3 = unable to do or not applicable). A higher score indicates worse physical function (Singh et al. 1994). Data will be captured on an electronic tablet.

The Discomfort Index of the CHAQ includes (Ruperto et al. 2001):

- Parent’s Global Assessment of Well-Being
 - This is a component of the PedACR core response set as well as the JADAS-27
 - The instrument is a 0 to 100 mm VAS assessing the current level of well-being where 0 = “Very well” and 100 = “Very poor”.
- Pain assessment due to illness
 - This instrument is a 0 to 100 mm VAS that assesses the current level of pain severity over the past week, where 0 = “No pain” and 100 = “Very severe pain”.

Childhood Health Questionnaire-Parent Form 50

The Childhood Health Questionnaire-Parent Form 50 (CHQ-PF50) is a generic observer-reported instrument designed to capture the health-related quality of life of children and adolescents (from 5- to 18-years of age), as well as the impact of the child's disease on the caregivers (HealthActCHQ 2013). The CHQ-PF50 is completed by the caregivers and has been validated for use in patients with JIA (Ruperto et al. 2001).

The CHQ-PF50 consists of 50 questions covering 14 health concepts: Global Health; Physical Functioning; Role/Social Limitations-Physical; Role/Social Limitations-Emotional/Behavioral; Bodily Pain/Discomfort; General Behavior; Mental Health; Self-Esteem; General Health Perceptions; Change in Health; Parental Impact-Emotion; Parental Impact-Time; Family-Activities; and Family-Cohesion.

Overall means for the individual CHQ scales and items will be scored according to the scoring manual. Scores will be transformed to ensure that all items are positively scored so that a higher score indicates better health (HealthActCHQ 2013). In addition, 2 summary scores, the Physical Summary Score (PhS) and Psychosocial Summary Score (PsS), will be evaluated based upon 10 scales of the CHQ-PF50. United States norms are available for the CHQ-PF50. The response options for the CHQ-PF50 vary from 4 to 6 levels for the scales. The majority of the items have a recall period of 4 weeks. Data will be captured on an electronic tablet.

European Quality of Life-Five Dimensions-Youth (EQ-5D-Y)

The EQ-5D-Y is a widely used, generic questionnaire that assesses health status "today" (The EuroQol Group 2014). It is completed by parents (proxy) for children aged 4 to 7 years; for children aged 8 years and older, the EQ-5D-Y will be self-completed (children aged <4 years will not complete this assessment per developer recommendation); respondents will continue with the version of the instrument they begin the study with even if they change age during the course of the study. The questionnaire consists of 2 parts: the first part assesses 5 dimensions (mobility, self-care, usual activities, pain/discomfort, and anxiety/depression) that have 3 possible levels of response (no problems, some problems, or a lot of problems). This part of the EQ-5D-Y can be used to generate a health state index score, which is often used to compute QALY for utilization in health economic analyses. The health state index score is calculated based on the responses to the 3 dimensions, providing a single value on a scale from less than 0 (where zero is a health state equivalent to death; negative values are valued as worse than dead) to 1 (perfect health), with higher scores indicating better health utility.

The second part of the questionnaire consists of a visual analog scale on which the patient rates their perceived health state from 0 ("the worst health you can imagine") to 100 ("the best health you can imagine"). Published studies by EuroQol Group members showed preliminary evidence of the instrument's feasibility, reliability, and validity (Ravens-Sieberer et al. 2010). The scale will be given to the parent/patient by the site investigator and self-completed by the parent/patient while they are at the site. The investigator will be responsible for checking for missing responses.

Morning Joint Stiffness Duration

As one of the assessments to determine inactive disease, the physician will ask the parent/legal guardian if the duration of their child's morning joint stiffness was >15 minutes since the previous visit; inactive disease is ≤15 minutes duration. Responses are yes/no.

Patient's Assessment of Pain Numeric Rating Scale (NRS)

The physician will ask the parent/legal guardian to rate their child's worst level of pain over the past week using a 0-10 NRS (0 = no pain; 10 = pain as bad as your child can imagine).

Product Acceptability and Palatability Assessments

The caregiver/legal guardian/patient will be asked to provide responses to questions designed to assess the acceptability and palatability of the formulations, either tablet or oral suspension. The questionnaire for tablet acceptability will assess the subject's ability to swallow the tablet. The questionnaire for suspension acceptability and palatability will assess the subject's experience relating to the taste and smell of the suspension and ease of administering and taking the suspension (Davies and Tuleu 2008; Kozarewicz 2014).

The appropriate questionnaire will be administered at baseline (after initial dose) and Visit 9 (after approximately 12 to 14 weeks of use). The questionnaire will be responded to by parents (proxy) for children aged 2 to 7 years. For children aged 8 years and older, the questionnaire will be self-completed.

9.1.6. Appropriateness of Assessments

All assessments utilized in this study are standard, widely used, and generally recognized as reliable, accurate, and relevant.

9.2. Adverse Events

Investigators are responsible for monitoring the safety of patients who have entered this study and for alerting Lilly or its designee to any event that seems unusual, even if this event may be considered an unanticipated benefit to the patient.

The investigator is responsible for the appropriate medical care of patients during the study.

Investigators must document their review of each laboratory safety report.

The investigator remains responsible for following, through an appropriate health care option, AEs that are serious or otherwise medically important, considered related to the investigational product or the study, or that caused the patient to discontinue the investigational product before completing the study. The patient should be followed until the event resolves or until the event stabilizes with appropriate diagnostic evaluation. The frequency of follow-up evaluations of the AE is left to the discretion of the investigator.

Lack of drug effect is not an AE in clinical studies, because the purpose of the clinical study is to establish treatment effect.

After the ICF and Assent Form (as applicable) are signed, study site personnel will record via electronic data entry the occurrence and nature of each patient's preexisting conditions, including clinically significant signs and symptoms of the disease under treatment in the study. In addition, site personnel will record any change in the condition(s) and any new conditions as AEs. Investigators should record their assessment of the potential relatedness of each AE to protocol procedure and/or investigational product, via electronic data entry.

The investigator will interpret and document whether or not an AE has a reasonable possibility of being related to investigational product, study device, or a study procedure, taking into account the disease, concomitant treatment, or pathologies.

A "reasonable possibility" means that there is a cause-and-effect relationship between the investigational product, study device, and/or study procedure and the AE.

The investigator answers yes/no when making this assessment.

Planned surgeries and nonsurgical interventions should not be reported as AEs unless the underlying medical condition has worsened during the course of the study.

If a patient's investigational product is discontinued as a result of an AE, study site personnel must report this to Lilly or its designee via electronic data entry, clarifying if possible the circumstances leading to discontinuations of treatment.

9.2.1. Serious Adverse Events

An SAE is any AE from this study that results in one of the following outcomes:

- Death
- Initial or prolonged in-patient hospitalization
- Life-threatening experience (i.e., immediate risk of death)
- Persistent or significant disability/incapacity
- Congenital anomaly/birth defect
- Important medical events that may not be immediately life-threatening or result in death or hospitalization but may jeopardize the patient or may require intervention to prevent one of the other outcomes listed in the definition above.

All AEs occurring after signing the ICF and Assent Form (as applicable) are recorded in the electronic data entry system and assessed for serious criteria. The SAE reporting to the sponsor begins after the patient has signed the ICF and Assent Form (as applicable) and has received investigational product. However, if an SAE occurs after signing the ICF and Assent Form (as applicable), but prior to receiving investigational product, the SAE should be reported to the sponsor as per SAE reporting requirements and timelines if it is considered reasonably possibly related to study procedure.

Study site personnel must alert Lilly or its designee of any SAE within 24 hours of investigator awareness of the event via a sponsor-approved method. If alerts are issued via telephone, they are to be immediately followed with official notification on study-specific SAE forms. This

24-hour notification requirement refers to the initial SAE information and all follow-up SAE information. Patients with a serious hepatic AE should have additional data collected using the electronic data entry system.

Pregnancy (during maternal or paternal exposure to investigational product) does not meet the definition of an AE. However, to fulfill regulatory requirements any pregnancy should be reported following the SAE process to collect data on the outcome for both mother and fetus.

Investigators are not obligated to actively seek AEs or SAEs in subjects once they have discontinued and/or completed the study (the patient disposition CRF has been completed). However, if the investigator learns of any SAE, including a death, at any time after a subject has been discontinued from the study, and he/she considers the event reasonably possibly related to the study treatment or study participation, the investigator must promptly notify Lilly.

9.2.1.1. Suspected Unexpected Serious Adverse Reactions

Suspected unexpected serious adverse reactions (SUSARs) are serious events that are not listed in the IB and that the investigator identifies as related to investigational product or procedure. United States 21 CFR 312.32 and European Union Clinical Study Directive 2001/20/EC and the associated detailed guidances or national regulatory requirements in participating countries require the reporting of SUSARs. Lilly has procedures that will be followed for the identification, recording, and expedited reporting of SUSARs that are consistent with global regulations and the associated detailed guidances.

9.2.2. Adverse Events of Special Interest

Adverse events of special interest will include the following:

- Infections (including TB, herpes zoster, or opportunistic infections)
- Malignancies
- Hepatic events (see Section 9.4.5)
- Major adverse cardiovascular events (MACE) (see Section 9.4.6)
- Venous thromboembolism (deep vein thrombosis and pulmonary embolism)
- Arterial thrombotic events (see Section 9.4.6)

Sites will provide details on these AEs as instructed on the eCRF and may be asked for additional description by Lilly.

9.2.3. Complaint Handling

Lilly collects product complaints on investigational products and drug delivery systems used in clinical studies in order to ensure the safety of study participants, monitor quality, and to facilitate process and product improvements.

Patients (or caregivers/legal guardians) will be instructed to contact the investigator as soon as possible if they have a complaint or problem with the investigational product so that the situation can be assessed.

9.3. Treatment of Overdose

Baricitinib single doses up to 40-mg and multiple doses of up to 20-mg daily for 10 days have been administered in clinical studies without dose-limiting toxicity. Pharmacokinetic data of a single dose of 40-mg in healthy volunteers indicate that >90% of the administered dose is expected to be eliminated within 24 hours. In case of an overdose, the patient should be monitored for signs and symptoms of adverse reactions. Patients who develop adverse reactions should receive appropriate treatment.

9.4. Safety

Any clinically significant findings from electrocardiogram (ECG) testing, physical examination, vital signs measurements, or laboratory measurements that result in a diagnosis and that occur after the patient receives the first dose of investigational product should be reported to Lilly or its designee as an AE via eCRF.

9.4.1. *Electrocardiograms*

A single 12-lead standard ECG will be obtained locally at screening and read by a physician qualified to read pediatric ECGs (the investigator or qualified designee) at the site to determine whether the patient meets entry criteria. Electrocardiograms may be obtained at additional times when deemed clinically necessary.

9.4.2. *Vital Signs*

For each patient, vital signs measurements should be conducted according to the Schedule of Activities (Section 2).

Any clinically significant findings from vital signs measurement that result in a diagnosis and that occur after the patient receives the first dose of study treatment should be reported to Lilly or its designee as an AE via electronic data entry.

9.4.3. *Laboratory Tests*

For each patient, laboratory tests detailed in [Appendix 2](#) should be conducted according to the Schedule of Activities (Section 2). Due to blood volume restrictions, some laboratory tests may not be collected. Laboratory samples are recommended to be collected as described in a sponsor-provided weight-based prioritization chart. Patients in the age cohort of age 2 to ≤7 years will not have flow cytometry testing due to blood volume limitations.

Use of local anesthetics (e.g., EMLA cream) consistent with local prescribing information is permitted during the study visit to ease discomfort associated with venipunctures. With the exception of laboratory test results that may unblind the study, Lilly or its designee will provide the investigator with the results of laboratory tests analyzed by a central vendor, if a central vendor is used for the clinical study.

Any clinically significant findings from laboratory tests that result in a diagnosis and that occur after the patient receives the first dose of investigational product should be reported to Lilly or its designee as AE via electronic data entry.

9.4.4. Hepatitis B Virus DNA Monitoring

Hepatitis B virus DNA testing will be performed in enrolled patients who tested positive for hBcAb at screening (refer to the Schedule of Activities in Section 2).

Patients who are hBcAb positive and HBV DNA negative (undetectable) at screening will require measurement of HBV DNA at Visit 9, Visit 12, Visit 15, Visit 17, ETV, and the follow-up visit, regardless of their hepatitis B surface antibody (hBsAb) status.

The following actions should be taken in response to HBV DNA test results:

- If a single result is obtained with a value “below limit of quantitation,” the test should be repeated within approximately 2 weeks.
- If the repeat test result is “target not detected,” monitoring will resume according to the study schedule.
- If the patient has 2 or more test results with a value “below limit of quantitation,” HBV DNA testing should be performed approximately once per month for the remainder of the study and referral to a hepatologist is recommended.
- If a result is obtained with a value above the limit of quantitation, at any time during the study, the patient will be permanently discontinued from investigational product (see Section 8.1.2) and should be referred to a hepatology specialist.
 - In selected cases, investigators may temporarily continue investigational product in accordance with current immunomodulator management in the setting of HBV DNA positivity. This option may be considered in consultation with Lilly (or its designee) and evaluation of individual patient risks and benefits.

9.4.5. Hepatic Safety Monitoring and Data Collection

If a study patient experiences elevated ALT ≥ 3 x ULN, ALP ≥ 2 x ULN, or elevated TBL ≥ 2 x ULN, liver testing ([Appendix 4](#)) should be repeated within 3 to 5 days including ALT, AST, ALP, TBL, direct bilirubin, gamma-glutamyl transferase, and creatine kinase to confirm the abnormality and to determine if it is increasing or decreasing. If the abnormality persists or worsens, clinical and laboratory monitoring should be initiated by the investigator and in consultation with the study medical monitor. Monitoring of ALT, AST, TBL, and ALP should continue until levels normalize or return to approximate baseline levels. Discontinuation criteria of investigational products, either temporary interruption or permanent discontinuation, due to abnormal ALT, AST, TBL, or ALP, are detailed in Section 8.1.

Additional safety data should be collected via the hepatic eCRF if 1 or more of the following conditions occur:

- ALT ≥ 5 x ULN confirmed by repeat testing
- ALP ≥ 2 x ULN confirmed by repeat testing
- TBL ≥ 2 x ULN confirmed by repeat testing (except for cases of known Gilbert’s syndrome)

- permanent discontinuation of investigational product due to hepatic event or hepatic lab abnormality
- hepatic SAE

Refer to [Appendix 4](#) for a description of hepatic laboratory values that warrant exclusion from the study, temporary or permanent discontinuation of investigational product (Section 8.1), or additional safety collection via the hepatic eCRF.

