- [41] Patients who are receiving thyroxine as replacement therapy may participate in the study, provided stable therapy has been administered for ≥ 12 weeks and thyroid-stimulating hormone (TSH) is within the laboratory's reference range.

Exception: Patients who are receiving stable thyroxine replacement therapy who have TSH marginally outside the laboratory's normal reference range may participate if the treating physician has documented that the thyroxine replacement therapy is adequate for the patient.

Diagnostic Assessments

[42] Have any of the following specific abnormalities on screening laboratory tests:

- AST or ALT ≥ 2 x upper limit of normal (ULN)
- Total bilirubin level (TBL) ≥ 1.5 x ULN
- Alkaline phosphatase (ALP) ≥ 2 x ULN
- Hemoglobin < 10.0 g/dL (100.0 g/L)
- Total white blood cell count < 3000 cells/ μ L ($< 3.00 \times 10^3$ / μ L or < 3.00 billion/L)
- Neutropenia (absolute neutrophil count [ANC] < 1500 cells/ μ L) ($< 1.50 \times 10^3$ / μ L or < 1.50 billion/L)
- Lymphopenia (lymphocyte count < 1000 cells/ μ L) ($< 1.00 \times 10^3$ / μ L or < 1.00 billion/L)
- Thrombocytopenia (platelets $< 100,000$ / μ L) ($< 100 \times 10^3$ / μ L or < 100 billion/L)
- eGFR < 40 mL/min/1.73 m² are excluded from enrolling in the study (Bedside Schwartz formula 2009 or The Japanese Society for Pediatric Nephrology formula for patients in Japan)
- eGFR < 60 mL/min/1.73 m² are excluded from the Safety/PK period of the study (Bedside Schwartz formula 2009 or The Japanese Society for Pediatric Nephrology formula for patients in Japan).

In the case of any of the aforementioned laboratory abnormalities, the tests may be repeated once during screening and values resulting from repeat testing may be accepted for enrollment eligibility if they meet the eligibility criterion.

[43] Screening laboratory test values, including TSH, outside the reference range for the population or investigative site that, in the opinion of the investigator, pose an unacceptable risk for the patient's participation in the study.

Prior/Concurrent Clinical Study Experience

[44] Currently enrolled in any other clinical study involving an investigational product or any other type of medical research judged not to be scientifically or medically compatible with this study.

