8.1. Discontinuation from Study Treatment

8.1.1. Temporary Interruption of Investigational Product

In some circumstances, patients may need to temporarily interrupt treatment as a result of AEs or abnormal laboratory values that may have an unclear relationship to investigational product. Except in cases of emergency, it is recommended that the investigator consult with Lilly (or its designee) before temporarily interrupting therapy for reasons other than those defined in [Table JAHV.7](#).

For the abnormal laboratory findings and clinical events (regardless of relatedness) listed in [Table JAHV.7](#), specific guidance is provided for temporarily interrupting treatment and when treatment may be restarted. Retest frequency and timing of follow-up laboratory tests to monitor the abnormal finding is at the discretion of the investigator. Investigational product that was temporarily interrupted because of an AE or abnormal laboratory value not specifically covered in [Table JAHV.7](#) may be restarted at the discretion of the investigator.

Table JAHV.7. Criteria for Temporary Interruption of Investigational Product

Hold Investigational Product if the Following Laboratory Test Results or Clinical Events Occur:	Investigational Product May be Resumed When:
WBC count <2000 cells/ μ L ($<2.00 \times 10^3/\mu$ L or <2.00 billion/L)	WBC count ≥ 3000 cells/ μ L ($\geq 3.00 \times 10^3/\mu$ L or ≥ 3.00 billion/L)
ANC <1000 cells/ μ L ($<1.00 \times 10^3/\mu$ L or <1.00 billion/L)	ANC ≥ 1500 cells/ μ L ($\geq 1.50 \times 10^3/\mu$ L or ≥ 1.50 billion/L)
Lymphocyte count <500 cells/ μ L ($<0.50 \times 10^3/\mu$ L or <0.50 billion/L)	Lymphocyte count ≥ 1000 cells/ μ L ($\geq 1.00 \times 10^3/\mu$ L or ≥ 1.00 billion/L)
Platelet count <75,000/ μ L ($<75 \times 10^3/\mu$ L or <75 billion/L)	Platelet count $\geq 100,000/\mu$ L ($\geq 100 \times 10^3/\mu$ L or ≥ 100 billion/L)
eGFR <40 mL/min/1.73 m ² (from serum creatinine) for patients with screening eGFR ≥ 60 mL/min/1.73 m ²	eGFR ≥ 50 mL/min/1.73 m ²
eGFR <30 mL/min/1.73 m ² (from serum creatinine) for patients with screening eGFR ≥ 40 to <60 mL/min/1.73 m ²	eGFR ≥ 40 mL/min/1.73 m ²
ALT or AST >5 x ULN	ALT and AST return to <2 x ULN, and IP is not considered to be the cause of enzyme elevation
Hemoglobin <8 g/dL (<80.0 g/L)	Hemoglobin ≥ 10 g/dL (≥ 100.0 g/L)
Symptomatic herpes zoster	All skin lesions have crusted and are resolving

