Infection that, in the opinion of the investigator, merits the IP being interrupted.	Resolution of infection that, in the opinion of the investigator, merits the IP being restarted.

Abbreviations: ALT = alanine aminotransferase; ANC = absolute neutrophil count; AST = aspartate aminotransferase; eGFR = estimated glomerular filtration rate; IP = investigational product; ULN = upper limit of normal; WBC = white blood cell.

8.1.2. *Permanent Discontinuation from Investigational Product*

Investigational product must be permanently discontinued if the patient or the patient's designee requests to discontinue investigational product.

Discontinuation of the investigational product for abnormal liver tests should be considered by the investigator after consultation with the Lilly-designated medical monitor when a patient meets 1 of the following conditions:

- ALT or AST >8 x ULN
- ALT or AST >5 x ULN for more than 2 weeks after temporary interruption of investigational product
- ALT or AST >3 x ULN and total bilirubin level (TBL) >2 x ULN or international normalized ratio (INR) >1.5
- ALT or AST >3 x ULN with the appearance of fatigue, nausea, vomiting, right upper-quadrant pain or tenderness, fever, rash, and/or eosinophilia (>5%)
- ALP >3 x ULN that is deemed to be of liver origin and drug-related
- ALP >2.5 x ULN and TBL >2 x ULN
- ALP >2.5 x ULN with the appearance of fatigue, nausea, vomiting, right upper-quadrant pain or tenderness, fever, rash, and/or eosinophilia (>5%)

Note: Patients who are discontinued from investigational product due to a hepatic event or liver test abnormality should have additional hepatic safety data collected via the hepatic safety eCRF.

Investigational product should be permanently discontinued if any of the following laboratory abnormalities are observed:

- White blood cell count <1000 cells/ μ L ($1.00 \times 10^3/\mu$ L or 1.00 billion/L)
- ANC <500 cells/ μ L ($0.50 \times 10^3/\mu$ L or 0.50 billion/L)
- Lymphocyte count <200 cells/ μ L ($0.20 \times 10^3/\mu$ L or 0.20 billion/L)
- Hemoglobin <6.5 g/dL (<65.0 g/L)

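### The 3-to-5-day liver retest and the hepatic eCRF are triggered by ALT but not AST, although the exclusion, hold and stopping rules use either enzyme

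*Protocol*

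**What the plan says.** Section 9.4.5 of the protocol starts the liver retest with "If a study patient experiences elevated ALT ≥ 3 x ULN, ALP ≥ 2 x ULN, or elevated TBL ≥ 2 x ULN". Once triggered, liver testing, with a pointer to Appendix 4, "should be repeated within 3 to 5 days including ALT, AST, ALP, TBL, direct bilirubin, gamma-glutamyl transferase, and creatine kinase". AST is therefore measured at the retest but cannot start it. The same section lists what opens the hepatic eCRF. Its only transaminase entry is "ALT ≥ 5 x ULN confirmed by repeat testing"; the other entries are confirmed ALP or TBL ≥2 × ULN, a permanent stop for a hepatic event or hepatic laboratory abnormality, and a hepatic SAE. The liver table in Appendix 4 agrees: its row is headed for both enzymes, but the cells for additional testing and for eCRF reporting name ALT only.

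The other rules use either enzyme:

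- Exclusion [42] in Section 6.2, introduced by "Have any of the following specific abnormalities on screening laboratory tests", uses AST or ALT ≥2 × ULN.
- Table JAHV.7 in Section 8.1.1 holds product at ALT or AST >5 × ULN.
- All four transaminase conditions in Section 8.1.2 name both, including "ALT or AST >3 x ULN and total bilirubin level (TBL) >2 x ULN or international normalized ratio (INR) >1.5" and "ALT or AST >3 x ULN with the appearance of fatigue, nausea, vomiting".

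For findings that lead to a hold, Section 8.1.1 says: "Retest frequency and timing of follow-up laboratory tests to monitor the abnormal finding is at the discretion of the investigator". No reason is given for leaving AST out of the two triggers.

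**The concern.** The protocol acts on AST when it excludes, holds or considers stopping, but not when it asks for early confirmation or for structured follow-up data. Section 3.3 reports rises in both enzymes in adults with RA on baricitinib, and Section 9.2.2 lists hepatic events as an adverse event of special interest.

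Two children with the same multiple of ULN are thus treated differently. If ALT is raised, the retest is due in 3 to 5 days. If only AST is raised, its timing depends on the investigator, although the value may already be half of a condition for considering a stop. At stake are prompt confirmation in a small number of children and, in fewer still, the detail on the hepatic form.

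**Working it through.** There is no stated figure to reproduce, so the check sets the rules side by side and walks an isolated AST rise through them.

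**Transaminase threshold rules in the protocol**

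| Rule | Place | Level (× ULN) | Enzyme |
|---|---|---|---|
| Exclusion | 6.2, criterion [42] | ≥2 | ALT or AST |
| Temporary hold | 8.1.1, Table JAHV.7 | >5 | ALT or AST |
| Consider stop | 8.1.2 | >8 | ALT or AST |
| Consider stop | 8.1.2 | >5 for more than 2 weeks after the hold | ALT or AST |
| Consider stop | 8.1.2 | >3 with TBL >2 × ULN or INR >1.5 | ALT or AST |
| Consider stop | 8.1.2 | >3 with symptoms or eosinophilia | ALT or AST |
| 3-to-5-day retest | 9.4.5, Appendix 4 | ≥3 | ALT only |
| Hepatic eCRF | 9.4.5, Appendix 4 | ≥5, confirmed | ALT only |

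Either enzyme: 6 of 8. ALT only: 2 of 8.

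**Isolated AST rise** (example: ALT 1.5 ×, ALP 1 ×, TBL 1 × ULN)

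| AST | Timed retest | Hold | eCRF on laboratory value | Stop conditions in play |
|---|---|---|---|---|
| 4 × | no | no | no | symptoms; INR >1.5 |
| 6 × | no | yes | no | as above; >5 × for more than 2 weeks after the hold |
| 9 × | no | yes | no | as above; >8 × |

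The bilirubin branch leaves no gap: TBL >2 × ULN always meets the TBL ≥2 × ULN retest trigger. The symptom branch can be recognised from the first result. The INR branch needs an INR.

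**Delay without a trigger.** Table JAHV.2 schedules clinical chemistry at every visit. From Week 4 on, visits are 28 days apart (Day 28, 56, 84 and so on). The fixed retest comes at 3 to 5 days, so the wait can be 28/5 = 5.6 to 28/3 = 9.3 times as long. The post-hold condition turns on 2 weeks (14 days). If the next value comes only at the next visit, it can come up to about 28 − 14 = 14 days after that point.

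**How wide the eCRF gap is.** AST >5 × ULN is held. Under Table JAHV.7 product may resume only when both enzymes are below 2 × ULN and product is not considered the cause. A rise attributed to product therefore cannot restart under that table and in effect ends in a permanent stop, which opens the form. AST still >5 × ULN more than 2 weeks into the hold is itself a condition for considering a stop. What mainly remains is confirmed AST ≥5 × ULN that resolves and is judged not drug-caused.

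**INR.** The retest sentence cites Appendix 4, which lists PT/INR, but INR is not among the 7 analytes it names (0 of 7), and Appendix 4 makes its tests permissive. INR is not in the routine list of Appendix 2. Appendix 8 does put it in the minimum local set for patients who cannot reach the site.

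**Cost in draws.** The documents give no frequency of isolated AST ≥3 × ULN, so the rates are assumptions. With N = 197, expected children = N × p and the chance of at least one = 1 − (1 − p)^197:

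| p | N × p | Chance of at least one |
|---|---|---|
| 0.5% | 0.98 | 0.63 |
| 1% | 1.97 | 0.86 |
| 2% | 3.94 | 0.98 |
| 3% | 5.91 | 1.00 |

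At one retest per affected child, that is about 1 to 6 additional draws in the whole study.

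**The case against.** The best case for the plan is that little escapes it. Section 9.2 has investigators document their review of each laboratory safety report. Appendix 2 allows unscheduled chemistry, and chemistry is scheduled at every visit anyway. The sponsor's physician follows laboratory trends (Section 9.4.6) and the DMC reviews laboratory data (Section 10.3.11). Section 9.4.5 itself refers to the stopping and hold criteria "due to abnormal ALT, AST, TBL, or ALP, are detailed in Section 8.1". Retest timing at the investigator's discretion applies to every finding in Table JAHV.7, not to AST in particular. AST can also come from muscle, so a trigger on ALT alone may be deliberate. All of this stands as a limit on the size of the point. It does not close the gap: for ALT, ALP and TBL the protocol sets a fixed interval and does not rely on discretion, and six rules already act on AST whatever its origin. Creatine kinase is in the retest panel and would help to identify a muscle source.

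A reader might infer more than the documents support:

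- *That AST rises go unmonitored or unreported.* They do not. SAP Section 6.18.5.1 tabulates AST at 3, 5 and 10 × ULN and profiles any patient with a single ALT or AST value ≥5 × ULN. It draws on the hepatic form only where one exists, so it allows for patients without one.
- *That an AST case cannot reach the eCRF.* It can, through a permanent stop for a hepatic laboratory abnormality or a hepatic SAE.
- *That INR is plainly optional, or decides a stop.* The pointer to Appendix 4 and the open-ended list make the text ambiguous. The liver conditions in 8.1.2 ask the investigator to consider stopping after consulting the medical monitor; they are not automatic.
- *That the protocol contradicts itself.* Section 9.4.5 and Appendix 4 agree with each other. The mismatch is with the rules for action.

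**Conclusion.** The point holds as a cheap improvement of low impact. Followed as written, an isolated AST rise (ALT <3 ×, ALP <2 ×, TBL <2 × ULN) gets no 3-to-5-day confirmation at any level. After Week 4 the next scheduled measurement is about 4 weeks away, even though AST >3 × ULN with symptoms or INR >1.5, or AST >5 × ULN for more than 2 weeks after a hold, is a condition for considering a stop. The eCRF gap is narrower still, and the missing mention of INR is a secondary clarification. No efficacy analysis is affected. The reading of the rules rests on the text alone. The number of children affected is unknown, and the 0.5% to 3% range is an assumption.

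**What to change.** 1. In Section 9.4.5 and the additional-testing cell of the Appendix 4 table, make the retest trigger *ALT or AST ≥3 × ULN*.
2. In the eCRF list of Section 9.4.5 and the eCRF cell of Appendix 4, make the entry *ALT or AST ≥5 × ULN*, still confirmed.
3. As a clarification, name PT/INR in the retest when a transaminase exceeds 3 × ULN, in line with the minimum set in Appendix 8.
4. If the ALT-only trigger was intended, give the reason in 9.4.5 instead of making changes 1 and 2.

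The text cost is a few words in 9.4.5 and two table cells. AST is already in routine chemistry, and Appendix 4 already provides for PT/INR by a local or sponsor-designated laboratory. The downside is about 1 to 6 extra draws under the assumed rates, some for AST of muscle origin. PT/INR samples at retests for raised transaminases come on top of that count, in children with limits on blood volume.
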